There will be two randomised groups:

- **A. Daily:** Children ingesting at least 2 peanuts daily.
- **B.** Weekly: Children ingesting at least 14 peanuts on one day once a week.

In both groups, children will be allowed to consume ad libitum additional peanuts or peanut protein in other food such as peanut butter/paste.

Treatment Supply:

All roasted peanuts for maintenance will be supplied by Flinders Proteomics Facility to participants, free of charge and in individually labelled containers. The Facility will also provide full quality control of peanuts.

Study Outcomes:

1. Primary outcome: Ongoing desensitisation to peanut as determined by successful completion of oral food challenge.

2. Secondary outcomes:

- Adverse events.
- Immunological changes in terms of serial skin Prick Tests, peanut-specific IgE and IgG4 levels. We are particularly interested to see if recurrent high-peak (weekly 14-peanuts) versus steady low-dose (daily 2 peanuts) can lead to different IgG4 levels.
- Parental questionnaires: Food Quality of Life; Depression, Anxiety and Stress Scale, Perceived Stress Scale; Food Allergy Quality of Life Burden Scale
- Child Questionnaires: Peanut Allergy Quality of Life; Revised Children's Anxiety and Depression Scale; Perceived Stress Scale for Children

Study Withdrawal:

Patients and children in either group can elect to stop eating peanuts altogether at any time during study and withdraw. Parents and children can elect to withdraw completely, or from just the questionnaires, and/or blood and skin prick tests. If they do they will be provided the opportunity to complete an exit questionnaire designed to understand why they have chosen to stop ingestion.

Ongoing Monitoring:

- Children and their parents will be interviewed face-to-face at baseline, 6 months and 12 months, when skin prick tests will be performed, blood samples taken for psIgE and psIgG4, mast cell activation tests, and questionnaires administered at Allergy SA.
- In addition, there will be two telephone calls to participants by the research assistant (RA) mainly for safety monitoring at 3 months and 9 months.
- Parents will also have the opportunity to contact RA any time if there is an adverse event, question, or change of mind in treatment continuation.

Otherwise, no further contact will be made to participants in order to ensure minimal interference with treatment adherence over the 12-month maintenance period.

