Special Transition for Group B Participants - from Daily to Weekly Ingestion:

- 1. Immediately after enrolment, subjects in Group B will increase their daily ingestion of peanuts from 12 per day to 14 per day over a 2 week period. They will then enter a transition phase, taking approximately 3 months to achieve:
- 2. Ingest peanuts every second day: on Day 1, 3, 5.
- 3. Ingest every third day: on Day 8, 11, 14.
- 4. Ingest every fourth day, on Day 18, 22, 26.
- 5. Ingest every fifth day, on Day 31, 36, 41.
- 6. Ingest every 6th day, on Day 47, 53, 59.
- 7. From Day 66 onwards: ingest once a week for the remaining treatment period of 12 months.
- 8. Patients are assessed at 3 months to see if the transition is successful.

9. An interim peanut challenge will be arranged at Allergy SA, after participants from this group have successfully transitioned from eating daily to eating weekly, within that 3-month period. This will be done before commencement of the next 9 months of weekly ingestion of roasted peanuts, to make sure that next phase of the study for this group of participants is safe.

Oral Food Challenges:

All oral food challenges will be undertaken at Allergy SA under direct supervision of the chief Investigator (BT), who is an experienced specialist allergist, and has performed such challenges regularly at his private practice, including those for the previous HYPES study, which had received full ethics approval. The site is fully equipped to deal with any anaphylactic emergency reaction during a challenge. Because participants were already eating 12 peanuts in one setting at the end of previous desensitisation study, this will also be the challenge dose for this study. All participants will be observed for 2 hours after the last dose of challenge. There will be 3 types of oral food challenges:

1. Interim food challenge at completion of transition for Group B (Weekly) participants:

o Before arrangements are made for the challenge, the RA will contact participants in Group B (weekly) to make sure that they are already eating 14 peanuts every day at home. The actual food challenge procedure is the same as the final OFC for Group B as detailed below

2. Special OFC schedule for Group A (daily) participants (in 3 days for increased safety):

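### The entry check for the weekly arm's interim challenge requires daily eating of 14 peanuts, but the challenge is placed after the move to weekly eating

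*Protocol*

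**What the plan says.** The Protocol (Treatment Schedules) defines the weekly arm as "Children ingesting at least 14 peanuts on one day once a week".

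The section on the special transition for Group B describes how children get there. In item 1, "subjects in Group B will increase their daily ingestion of peanuts from 12 per day to 14 per day over a 2 week period". The text goes on: "They will then enter a transition phase, taking approximately 3 months to achieve" the steps that follow. Item 2 ends daily eating: "Ingest peanuts every second day: on Day 1, 3, 5". Items 3 to 6 widen the interval to three, four, five and six days. Item 7 reads "From Day 66 onwards: ingest once a week for the remaining treatment period of 12 months".

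Item 9 schedules an interim peanut challenge "after participants from this group have successfully transitioned from eating daily to eating weekly", inside the 3-month period. It adds: "This will be done before commencement of the next 9 months of weekly ingestion of roasted peanuts". The stated purpose is to make sure that the next phase is safe for this group.

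The Oral Food Challenges section lists this challenge first, under a heading that also ties it to the end of the transition. Directly beneath, it says that before the challenge is arranged the research assistant will contact Group B participants "to make sure that they are already eating 14 peanuts every day at home".

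**The concern.** The check and the challenge refer to different stages of the schedule. Eating 14 peanuts every day describes a child at the end of the run-in, one day after the previous dose. The challenge is meant for a child on weekly eating, seven days after the previous dose.

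At stake is whether this safety step does its job. Staff who apply the sentence as written would hold back the children who completed the transition. If they instead challenged children still eating daily, the result would say nothing about tolerance after a seven-day gap, which is the condition those children would then live under at home.

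**Working it through.** No alpha, power or effect size enters. The check is day arithmetic on the stated schedule, followed by a comparison of the passages.

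**Inputs (Protocol, special transition for Group B):** a 2-week run-in (14 days) up to 14 peanuts a day; then transition Days 1, 3, 5; 8, 11, 14; 18, 22, 26; 31, 36, 41; 47, 53, 59; and weekly from Day 66. Group size, 30 per arm out of 60, is from the power calculation.

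**Step 1: reproduce the plan's own figure.** Start with Days 1, 3, 5 (2-day gaps) and add three doses at each longer gap:
- 3 days: 5 + 3 = 8, then 11, 14
- 4 days: 14 + 4 = 18, then 22, 26
- 5 days: 26 + 5 = 31, then 36, 41
- 6 days: 41 + 6 = 47, then 53, 59
- 7 days: 59 + 7 = 66

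This gives Day 66, as stated. The schedule itself is consistent.

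**Step 2: place it on the enrolment clock.** The transition follows the run-in, so weekly eating starts at about 14 + 66 = day 80 (80 / 30.4 = 2.6 months). Daily eating of 14 ends at about day 14, which is 80 − 14 = 66 days earlier.

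**Step 3: locate the challenge.** Item 9 puts it after weekly eating is reached and within the 3-month period. Taking 3 months as 91 days from enrolment, that is roughly day 80 to day 91, with weekly doses at about days 80 and 87. If the 3 months run from the start of the transition, the window extends to 14 + 91 = day 105. Either way, it opens about 66 days after daily eating should have ended.

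**Step 4: compare the states.**

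| | Entry check, read literally | Group B after the transition |
|---|---|---|
| Frequency | every day | once a week |
| Gap since last dose | 1 day | 7 days |
| Peanuts per week | 7 × 14 = 98 | at least 14 |
| When the schedule has it | end of run-in, about day 14 | from about day 80 |

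No point on the schedule meets both columns.

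**The case against.** The best defence is that the words about every day are a drafting slip. Item 9, the challenge heading, the definition of Group B and items 2 to 7 all have the child on spaced or weekly eating by then. The requirement of full adherence in the preceding 2 weeks, stated alongside the final challenge, points the same way. Staff who know the study would probably read past the sentence. That is a fair account of how the error arose, and it makes any actual mishandling uncertain. It does not remove the error: the sentence is the instruction for the check, and nothing else in the Protocol corrects it.

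Two rescuing readings fail. The contact might be meant for the end of the run-in, but it sits under a heading about the completed transition, and it would then verify nothing about that transition. Peanuts beyond the schedule are allowed freely in both groups, so a Group B child could in fact eat 14 a day. Such a child would still be exposed daily and would not meet item 9's condition.

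A reader might also infer more than the Protocol supports:
- **That items 7 and 9 conflict over weekly eating starting before the challenge.** Item 9 expects weekly eating to have begun; the challenge precedes the following 9 months of it.
- **That a 12-peanut challenge contradicts the 14-peanut home amount.** The Protocol gives its reason for 12, namely what children were eating at the end of the previous study, and applies it to all challenges.
- **That this is the only safety gate.** Item 8 assesses the transition at 3 months, there are safety calls at 3 and 9 months, and parents may make contact at any time.
- **That the check decides who stays in the weekly arm or in the primary denominator.** The Protocol does not say what follows a failed check or interim challenge, and it states intention-to-treat analysis.

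**Conclusion.** The entry check is wrong as written. It contradicts item 9 and the heading it stands under, and taken literally it selects children who have not reached the state the challenge is meant to clear. It applies to all of Group B, about 30 of the planned 60 children, and to their only supervised challenge between baseline and the final one. The mismatch is a daily against a seven-day interval, with weekly eating starting about 66 days after daily eating ends.

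This rests on transition Day 1 following directly after a 14-day run-in, and on a child who eats by the schedule without enough extra peanuts to amount to daily dosing. The effect is confined to the interim safety procedure: neither the primary analysis nor the power statement uses this check.

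**What to change.** The investigators should decide which dosing state the check is meant to confirm. They should then amend the Protocol so that the check, item 9, the challenge heading and the Group B schedule all describe that state. Which passage should give way is their clinical decision, and no dose, interval or entry rule is proposed here. The cost is one short clarification or amendment, with no added visits or participants.

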
Project Design

Methodological Approach:

The design will be a Randomised Controlled Trial with 3 study visits - at baseline, 6 months and 12 months respectively. There will also be 2 phone calls at 3 months and 9 months.

Participants:

All children successfully desensitised in Phase-II clinical will be invited to participate in this project. Subjects who had failed to be desensitised, or had withdrawn from the previous trial, will not be eligible for this randomised study. Based on feedback from research assistant (RA) of the previous trial we expect at least 60 interested participants.

Invitation to participate and collection of signed consent (PICF):

The Research Assistant (RA), who was involved in the HYPES study and therefore knew very well the children and their family members from the old study, will contact potential participants of this new study by phone, and invite them to participate again. A telephone script for the recruitment has been drafted, and the document will be uploaded for ethics approval.

After the telephone invitation, if parents of children showed interest in the new trial, an appointment will be made for the RA to meet the respondents, at Allergy SA. To avoid conflict of interest, [name] will not be present at the meeting, which will take about an hour to allow adequate time for explanation.

The parents/caregivers will take the PICF home to study, and discuss among family members, friends and third party individuals such as their family doctors, and this will include the children themselves. A follow-up phone call from the RA will be made within 2 weeks.

A separate consent will be obtained from parents/caregivers and older participating children if they want to be involved in the decision making.

Randomisation:

Treatment will be assigned with the help of a computer-generated randomisation schedule (using www.randomization.com), with treatment assignment concealed in opaque envelopes. Due to the nature of the study it will not be possible to blind the clinician, parents/carers or child to treatment allocation. Randomisation will be into one of the two treatment schedules, stratified by whether the child likes or dislikes eating peanuts.

Treatment Schedules:

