- o On day 1: At Allergy SA, subjects will ingest 2 peanuts soon after arrival, wait for ½ hour, then another 2 peanuts, wait for another ½ hour and, if no adverse reaction, ingest the last 2 peanuts, making a total of 6 peanuts cumulatively on Day 1. Subjects will be observed for two hour before discharge.
- On day 2: After arrival, subjects will ingest a single dose of 6 peanuts, wait for ½ hour, then 2 more peanuts, wait for another ½ hour, then another 2 peanuts, wait for another ½ hour, then finally the last 2 peanuts, making a total of 12 peanuts cumulatively on Day 2. Subjects will be observed for two hour before discharge.
- On day 3: subjects will be witnessed to ingest 12 peanuts as a single dose, and then observed for two hour before discharge. Success at OFC indicates that the participants have maintained their protection 12 months after desensitisation.

3. OFC for Group B (weekly) participants:

 Subjects will be witnessed to ingest 12 peanuts as a single dose at Allergy SA, thus confirming that they have maintained their protection 12 months after desensitisation.

The decision to proceed with the final OFC is made, and then arranged, at the last visit of the 12-month study period. A prerequisite for OFC is that participants must be fully-adherent to the protocol in the preceding 2 weeks. For the weekly group (Group B) they will simply return at the next scheduled ingestion date and be witnessed eating 12 peanuts at Allergy SA. For the daily group (Group A), it will be a 3-day event as explained above.

Psychological Measures and Questionnaires:

Questionnaires will be administered to measure quality of life, depression and anxiety, as well as stress factors among children and parents throughout study. These questionnaires have all been well-validated in their target population of children or parents, and will be administered to both groups.

We intend to investigate the relationship between psychological measures and treatment adherence and satisfaction. The depression, anxiety, and stress measures will be used to investigate any relationship with adherence and quality of life.

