The questionnaires will be printed in hard copies and administered to parents at Baseline, 6-months and 12-months respectively at Allergy SA, at the same interview when skin tests are also performed and blood samples taken. Some questionnaires will be completed at the site but the remaining unanswered questions will be allowed to take home and be answered at a more leisurely pace. Parents will be given a pre-addressed and reply-paid envelope to send the answers back to the RA, who will check with parents if she has not received the envelope after 2 weeks.

The following are the lists of questionnaires:

Children:

- Quality of life Peanut allergy PedQL (Pediatr Allergy Immunol 2003;14:378);
- **Depression and anxiety scores -** Revised Children's Anxiety and Depression Scale (RCADS), (https://www.corc.uk.net/outcome-experience-measures/revised-childrens-anxiety-and-depression-scale-and-subscales/)
- Stress Perceived Stress Scale for children (PSSC), (https://www.researchgate.net/publication/277630701_The_Perceived_Stress_Scale _for_Children_A_Pilot_Study_in_a_Sample_of_153_Children).

Parents:

- Quality of life
 - o Food Quality of Life Questionnaire Parent Form (DunnGalvin et al 2008)
 - o Food Allergy Quality of Life Parental Burden Scale (Cohen et al 2004)
- **Depression and anxiety scores** Depression, Anxiety, and Stress Scale (DASS) (Lovibond & Lovibond, 1995).
- Stress perceived stress scale (PSS).

Sample Size and Statistical Analysis:

- Analysis will be undertaken according to intention-to-treat principle.
- Dichotomous outcomes, including successful completion of oral food challenges, proportion experiencing adverse effects, and adequate treatment adherence, will be assessed by calculating a risk ratio (RR) with 95% CI, determined with a log-binomial model.
- Food related QOL at end of trial will be compared between groups using linear-mixed models, adjusting for food related QOL.
- Appropriate statistical analyses for immunological parameters will be undertaken according to underlying distribution of each variable (i.e. IgE, IgG4, skin pricks). Differences between groups at baseline, 6 months and 12 months will be compared using *Two Sample t-Test* or *Wilcoxon Rank Sum Test* for parametric and non-parametric data respectively. Differences within group across time will be compared

using *Paired t-Test* or *Wilcoxon Signed Ranks Test* for parametric and non-parametric data respectively.

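### Take-home completion lets some 12-month questionnaire items follow the final challenge, and possibly some baseline items follow open allocation, which could bias the secondary quality-of-life comparison

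*Protocol*

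**What the plan says.** The Protocol section on Psychological Measures and Questionnaires has paper forms "administered to parents at Baseline, 6-months and 12-months respectively at Allergy SA". Some are completed on site. For the rest, "the remaining unanswered questions will be allowed to take home and be answered at a more leisurely pace", and they are posted back to the research assistant, "who will check with parents if she has not received the envelope after 2 weeks". The section gives no completion date, no final return limit, and no list of the scales that must be finished at the visit.

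Four other places bear on timing:

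- **Randomisation:** assignments are in opaque envelopes, and "it will not be possible to blind the clinician, parents/carers or child to treatment allocation". When the envelope is opened is not stated.
- **Special Transition for Group B:** "Immediately after enrolment, subjects in Group B will increase their daily ingestion of peanuts", from 12 to 14 a day over two weeks. Spacing of doses starts only after that.
- **Oral Food Challenges:** "The decision to proceed with the final OFC is made, and then arranged, at the last visit of the 12-month study period". Group B then attends on its next weekly ingestion date. Group A has a three-day procedure with no stated interval from the visit. Full adherence in the preceding 2 weeks is a prerequisite.
- **Sample Size and Statistical Analysis:** end-of-trial food-related quality of life is compared "using linear-mixed models, adjusting for food related QOL". The covariate is presumably the baseline value, but the text does not say so.

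**The concern.** A baseline measurement should precede knowledge of the arm, and an end-of-trial measurement should precede events that are not part of what it measures. The take-home rule secures neither.

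If a baseline score already carries a reaction to the allocation, adjusting for it removes or distorts part of the arm effect. If a 12-month score is given after the child has passed or failed the challenge, it mixes life on the regimen with relief or disappointment at the result.

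The Protocol's own reasoning makes both effects plausible. Its background section suggests that the period just after desensitisation may be a turning point for quality of life, and that successful desensitisation can ease anxiety.

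The outcomes at stake are secondary: quality of life, and by the same route anxiety, depression and stress. The primary challenge outcome is not affected.

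**Working it through.** The Protocol gives no figure to reproduce on this point. The check sets the return window against the visit, dosing and challenge timeline, and then sizes the baseline mechanism under stated assumptions.

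**12-month forms**

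1. Forms are handed out at the 12-month visit (day 0). The first check on missing forms comes after day 14.
2. The final challenge is arranged at that visit, so it comes later. In Group B it is on the next weekly date, by about day 7. Since 7 < 14, a form returned with no chasing can follow the challenge.
3. In Group A the interval is not stated, so overlap is possible but cannot be dated.
4. Let s be the share of a group answering after the challenge and c the mean shift in score that this causes. The distortion of the arm difference is s_B × c_B − s_A × c_A. It is zero if the products are equal. They may differ, because the procedures differ (single dose against three days), the dates may differ, and only recently adherent children are challenged while hypothesis 4 expects adherence to differ by arm. The Protocol gives no value for s or c, so no size is offered.

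**Baseline forms**

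1. Group B's increase lasts two weeks from enrolment, the same length as the return window.
2. Group A moves from 12 peanuts in one sitting at the end of the previous study to at least 2 daily. Its start date is not stated.
3. If the envelope is opened at or near the baseline visit, a form finished at home can therefore be answered knowing the arm and during changed intake.

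**Size of the baseline part.** The inputs are assumptions, not document values: ρ is the slope of final on baseline score, s the share answering after allocation, and e the early shift between arms in SD. The bias in the adjusted difference is −ρ × s × e.

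| ρ | s | e (SD) | Size of bias (SD) |
|---|---|---|---|
| 0.5 | 0.3 | 0.2 | 0.03 |
| 0.7 | 0.6 | 0.4 | 0.168, about 0.17 |
| 0.3 | 0.25 | 0.1 | 0.0075, about 0.01 |
| 0.7 | 1 | 0.5 | 0.35 |

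The first two rows bound the main range; the last two bound a wider one.

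For scale, with 30 per arm (the Protocol's figure):

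- Unadjusted standard error: √(2/30) = 0.26 SD.
- Adjusted standard error at ρ = 0.7: 0.258 × √(1 − 0.49) = 0.18 SD.
- Difference detectable with 80% power, two-sided 5%: (1.96 + 0.84) × 0.258 = 0.72 SD unadjusted, or 0.52 SD adjusted at ρ = 0.7.

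A simulation with no true arm effect, 30 per arm and 20,000 replicates agrees with the formula:

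| ρ, s, e | Mean bias (SD) | Type I error |
|---|---|---|
| 0.5, 0, 0.3 (all forms before allocation) | 0.00 | 5.1% |
| 0.5, 0.5, 0.3 | −0.08 | 6.0% |
| 0.7, 1, 0.3 (extreme) | −0.21 | 19% |

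**The case against.** The strongest reply concerns the baseline part. A reader might infer that baseline forms finished at home are necessarily answered knowing the arm, since there is no further scheduled visit before 6 months at which to allocate. The text does not support that. Allocation needs no visit, the research assistant already works by telephone, enrolment is not tied to the baseline visit, and the flow chart is not available. Opening the envelope after the forms return is compatible with the Protocol. This stands, so the baseline part is conditional. Even so, no statement in the Protocol requires that order.

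Second, weekly ingestion has not begun in the return window: Group B still eats daily in those two weeks. An early arm effect could come from knowing the arm or from Group A's lower minimum intake, but it is not shown. This also stands.

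Third, a reader might infer that 12-month scores no longer measure life on the regimen. That goes too far. Only items taken home and answered late are affected, some forms are completed on site, and the quality-of-life scales may be among them. Both arms face a challenge after the last visit, so a difference between arms is possible but not demonstrated.

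Fourth, completion dates and form order may sit in a study manual or on the forms. That is possible. But the take-home rule is stated in the Protocol, and if forms are undated no later analysis can identify the late ones.

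Finally, taking forms home eases the burden on families and may reduce missing data. The fix should keep that where it does no harm.

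**Conclusion.** The timing gap is real and is firmest at 12 months, where following the stated rule allows Group B items to be answered after the challenge. At baseline it depends on the envelope being opened at or near the visit.

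The document supports saying that the open-label comparison of secondary quality-of-life outcomes could be biased, not that it is biased. Bias requires late completion by some respondents and an effect that differs between arms; if either is absent, the bias is zero. The direction cannot be derived.

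The range of 0.03 to 0.17 SD for the baseline part rests wholly on an assumed slope, share and shift, and on the covariate being baseline quality of life. It lies below the unadjusted standard error of 0.26 SD, and its upper end is just under the adjusted one of 0.18 SD. The case for change is that the remedy is cheap and must be in place when the data are collected.

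**What to change.** In Psychological Measures and Questionnaires:

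- Have at least the food-related quality-of-life scales completed and handed in before the allocation envelope is opened.
- Have the same scales completed at the 12-month visit, or otherwise before the first dose of the final challenge.
- Record the completion date on every form, so that late forms can be identified and set aside in a sensitivity analysis.
- Let the other scales still be taken home, and leave the 6-month arrangement as it is.
- State that families who decline questionnaires, as Study Withdrawal allows, still proceed to allocation and challenge. The primary outcome must not depend on a secondary-outcome form.

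The Randomisation section should say when the envelope is opened relative to the baseline forms.

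The cost is a slightly longer visit, or an envelope opened only once the forms are back, perhaps about two weeks later. No new instrument or visit is needed, and no sample size, dose or challenge procedure changes.

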Peanut allergy affects up to 3% of Australian children and in most cases is a life-long condition. Desensitisation, while not a cure, is the only proactive and disease-modifying therapeutic approach currently available. Oral immunotherapy (OIT) is the most effective desensitisation method but is hampered by high rates (45-93%) of adverse events (AEs). Preliminary data from 69 children currently participating in our Phase 2 clinical trial of sequential boiled-to-roasted peanut OIT, funded by Channel 7 Children's Research Foundation in 2017-18, suggest that our unique OIT method is effective and has a low AE rate.

However, desensitisation using OIT can only confer temporary protection and requires ongoing peanut maintenance consumption, typically for many years or even life-time. Limited published data available have indicated that adherence to maintenance peanut consumption is poor, but the dearth of good studies has been a major limitation in the evaluation of long-term utility of existing randomised controlled trial evidence. Also, current data have provided no insight on the reasons for, or solutions to, the important problem of non-adherence.

With impending completion of our Phase 2 clinical trial on peanut oral immunotherapy in early 2019, we are well-positioned to investigate if we can observe improved adherence to peanut consumption in any one of the two different regimens and arrive at possible reasons for non-adherence. Through randomisation we aim to determine whether allocating children to either daily or weekly peanut ingestion as post-desensitisation maintenance is associated with measurable differences with respect to:

- Ongoing peanut desensitisation as determined by oral food challenges
- Immunological changes as indicated by serial skin prick tests, serum levels of peanut-specific IgE and IgG4, and mast cell activation tests
- Treatment adherence and continuation of peanut ingestion for 12-months;
- Quality of Life, treatment satisfaction and adverse events.

Hypothesis and Expected Outcomes

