• A p-value of less than 0.05 will be considered to indicate statistical significance.

Power calculation:

The overall sample size is capped according to the number of children who have complete the original HYPES study. HYPES enrolled 69 children and we estimate that 60 of these would consist to this post-HYPES study. While the sample is small, this study will provide critical data to inform the development of larger clinical trials and demonstrate the feasibility of evaluating outcomes associated with ongoing maintenance regimens following successful peanut desensitisation. Based on the limited number of eligible children, a total of 60 participants (30 in each group) would provide 80% power (alpha 0.05) to detect an absolute difference of 25% with respect to successful completion of OFC or non-adherence/withdrawal from treatment. Previous literature and our own clinical experience indicates that non-adherence to peanuts is a major problem, with 33-62% of children becoming non-adherent within 12-36 months of successful peanut desensitisation. Therefore our study is sufficiently powered to determine whether frequency of peanut ingestion is associated with a 25% or greater difference with respect to treatment adherence.

Flow Chart

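### The between-arm tests of IgE, IgG4 and skin prick results leave out the baseline value already collected, losing precision at no saving; the arms are also tested at baseline, and change only within each arm

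*Protocol*

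**What the plan says.** All references are to the Protocol.

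- **Which markers.** The analysis bullet in Sample Size and Statistical Analysis reads "Appropriate statistical analyses for immunological parameters will be undertaken according to underlying distribution of each variable (i.e. IgE, IgG4, skin pricks". It names three, as does the secondary outcome in Study Outcomes: "Immunological changes in terms of serial skin Prick Tests, peanut-specific IgE and IgG4 levels". Research Questions and Aims lists four: "Immunological changes as indicated by serial skin prick tests, serum levels of peanut-specific IgE and IgG4, and mast cell activation tests". Ongoing Monitoring schedules all four at baseline, 6 and 12 months.
- **Between arms.** Differences "at baseline, 6 months and 12 months will be compared using" a two-sample t-test or Wilcoxon rank sum test, depending on distribution. No covariate is named.
- **Within arms.** Differences within group "across time will be compared" by paired t-test or Wilcoxon signed ranks test.
- **Threshold.** "A p-value of less than 0.05 will be considered to indicate statistical significance".
- **Emphasis.** Study Outcomes states a particular interest in whether recurrent high weekly peaks "versus steady low-dose (daily 2 peanuts) can lead to different IgG4 levels".
- **QOL.** End-of-trial food related quality of life is compared between groups using "linear-mixed models, adjusting for food related QOL". No time point is given for the covariate.
- **Stratum.** Randomisation is stratified by whether the child likes or dislikes peanuts. The analysis bullets do not mention this factor.

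**The concern.** The aims ask whether allocation to daily or weekly ingestion is associated with differences in immunological change. The plan answers in two disconnected parts. The between-arm tests compare levels at a visit and ignore where each child started. The change tests use the starting value but do not compare the arms. No planned test compares the arms while taking account of baseline.

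Three consequences follow.

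1. **Lost precision.** Where a marker tracks within a child, part of the spread at 12 months was already present at baseline. Leaving that spread in the error term widens the interval on the IgG4 contrast. The Protocol itself describes the sample as small and capped by the number of children who completed the earlier trial. Its third hypothesis expects similar profiles in the two arms, so a wide interval with p above 0.05 could easily be taken as support.
2. **Tests at baseline.** Under randomisation any baseline difference arises by chance. A significance test there answers no question and can produce a spurious imbalance.
3. **Within-arm tests.** A significant change in one arm and not in the other is easily mistaken for a difference between arms.

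**Working it through.** **The plan's own figure.** None exists for this comparison. The only power statement (80% for a 25-point absolute difference) concerns the binary outcomes, so there is nothing to reproduce for the markers.

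**Inputs**
- 30 per arm, from the Power calculation section. This is a best case, because families may withdraw from the blood and skin tests.
- Threshold 0.05, from the analysis section; two-sided is assumed.
- Baseline-to-follow-up correlation r: not in the Protocol. Assumed range 0.3 to 0.8.
- Three markers named in the analysis bullet.

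**Step 1: follow-up-only comparison, as planned.** Normal approximation, in units of the between-child SD at follow-up:

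detectable difference = (1.960 + 0.842) × √(2/30) = 2.802 × 0.258 = 0.72 SD at 80% power. (The t distribution gives 0.74.)

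**Step 2: with baseline as covariate.** Residual variance is multiplied by 1 − r², and the detectable difference and CI width by √(1 − r²). Equivalent unadjusted size per arm is 30/(1 − r²). The small cost of estimating the slope is ignored.

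| r | Variance cut | CI narrower by | Detectable at 80% power | Power for a true 0.5 SD difference | Equivalent n per arm |
|---|---|---|---|---|---|
| as planned | – | – | 0.72 SD | 49% | 30 |
| 0.3 | 9% | 5% | 0.69 SD | 53% | 33 |
| 0.5 | 25% | 13% | 0.63 SD | 61% | 40 |
| 0.7 | 49% | 29% | 0.52 SD | 77% | 59 |
| 0.8 | 64% | 40% | 0.43 SD | 90% | 83 |

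**Step 3: chance imbalance.** The standard error of a baseline difference is √(2/30) = 0.26 SD. A one-standard-error imbalance, with r = 0.7, shifts the unadjusted 12-month contrast by 0.7 × 0.26 = 0.18 SD. Over repeated randomisations such shifts average to zero, and the test keeps its 5% error rate.

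**Step 4: baseline tests.** Three tests at 0.05, if independent, give 1 − 0.95³ = 0.14 as the chance of at least one spurious imbalance. Independence is doubtful for IgE and skin test results in the same child, so this is a guide only.

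**Step 5: within-arm tests.** If both arms truly change by the same amount and each paired test has power p, exactly one arm is significant with probability 2p(1 − p). This is 0.50 at p = 0.5 and 0.32 at p = 0.8.

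**The case against.** The strongest reply is that a two-sample comparison of follow-up values in a randomised trial is valid. That stands. A reader might infer that the planned tests are biased or inflate the false positive rate. They do neither: the overall error rate is 5%, and the complaint is about efficiency.

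Other limits also stand.

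- **Size.** The Protocol supplies no r. At r = 0.3 the gain is slight (0.72 to 0.69 SD). The 1 − r² formula also does not carry over exactly to rank tests.
- **Use of baseline.** One might say that the plan discards the baseline value. That goes too far, since the paired tests can use it. It is missing only from the between-arm comparison.
- **Number of markers.** The aims might suggest that four markers are tested this way. The analysis bullet names three. Mast cell activation is an aim and is measured, but no analysis is assigned to it.
- **Scale.** The bullet lets the analysis follow each marker's distribution, so transformation is left open. The text does not commit to untransformed values.
- **Within-arm tests.** The plan lists within-group and between-group differences separately and nowhere says that the former will be used to compare arms. The risk lies in interpretation.
- **QOL.** Read literally, the sentence adjusts end-of-trial QOL for itself. The questionnaires are administered at baseline, 6 and 12 months, so the likely explanation is a missing word, not an intended wrong model.

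Detailed covariate lists may be left to an analysis plan. Here, however, the Protocol names the tests itself, and they contain no baseline term.

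**Conclusion.** The point holds as one of avoidable imprecision in secondary outcomes. The between-arm tests for IgE, IgG4 and skin pricks are valid but leave out a baseline measurement that the trial already takes, and the IgG4 question is answered less precisely than the data allow. Over an assumed r of 0.3 to 0.8, the detectable difference would fall from 0.72 SD to between 0.69 and 0.43 SD. Where in that range the true gain lies cannot be told from the Protocol. The figures rest on 30 analysed children per arm, two-sided 0.05 and a roughly linear relation between baseline and follow-up on the analysis scale.

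The baseline significance tests serve no purpose, and the within-arm tests cannot support a statement about the arms. The QOL sentence needs a wording correction only. The primary outcome, oral food challenge success analysed by a log-binomial risk ratio, is not affected.

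**What to change.** 1. Compare each marker between arms at 6 and 12 months with an ANCOVA or a mixed model that has the baseline value and the like/dislike stratum as covariates. Transform the marker, or use a rank-based version, where its distribution requires. Report the 12-month arm difference with its 95% CI.
2. Describe the baseline values by arm without significance tests.
3. Present within-arm changes descriptively, and state that they are not evidence of a difference between arms.
4. In the QOL sentence, insert the word baseline before the covariate.
5. State whether mast cell activation is compared between arms and, if so, use the same model.

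The cost is a change of wording. The baseline measurements and the stratum are already collected, so no new data, visits or participants are needed.
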